**FAMILY SCREENING**

**ID SUBJEK :**

**NAMA SUBJEK:**

No	Nama anggota keluarga	ID	BB	Suhu	Demam seminggu terakhir (Y/T)	LMF	LMS	Filter paper
1						Malam:	Malam:	Malam:
						Siang:	Siang:	Siang:
2						Malam:	Malam:	Malam:
						Siang:	Siang:	Siang:
3						Malam:	Malam:	Malam:
						Siang:	Siang:	Siang:
4						Malam:	Malam:	Malam:
						Siang:	Siang:	Siang:
5						Malam:	Malam:	Malam:
						Siang:	Siang:	Siang:

**CASE REPORT FORM**

**ID :**

**NAMA:**

**L/P**

**FAMILY SCREENING/SEKOLAH:**

**G6PD:**

**HASIL: *P. FALCIPARUM / P.VIVAX / P. MALARIAE / P. OVALE***

Hari	D-1	D-2	D-3	D-4	D-5	D-6	D-7	D-8	D-9	D-10	D-11	D-12	D-13	D-14
Tanggal														
DHP (jml tablet)														
Primakuin (jml tablet)														
Hb (D-1 sebelum minum obat & D-3)														
Urin (D-1 sebelum minum obat)														
Keluhan														
Alergi														
Pusing														
Sakit kepala														
Bibir kebiruan														
Keluhan di dada														
Mual														
Muntah														
Gangguan napsu makan														
Gangguan Buang Air Besar (BAB)														
Gangguan Buang Air Kecil (BAK)														
Gangguan tidur														
Tanda tangan pasien														
Tanda Tangan Petugas Pengawas Minum Obat														
Tanda Tangan Manajer Site/Wakil

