### **6.8. Antimalarial treatment**

Treatment will be provided based on body weight (Appendix B). Blood schizonticide for any species is 3-day DHA-PP (daily dose: 6-10 kg=1/2 tab, 11-17 kg=1 tab, 18-30 kg=1 ½ tab, 31-40 kg=2 tab). For *P. vivax* subjects, the administration of high dose primaquine will be started at the same day of DHA-PP treatment (see Table 2 appendix B for PQ dosage). Meal should be given prior to PQ administration daily. The total dose of PQ should be completed within 10 days as the window period. Subjects who does not complete the dose will be recorded, and still be followed until end of study. Monitoring of Hb level and hemoglobinuria for treated subjects will be done daily before and during treatment by Hb measurement using HemoCue (HemoCue AB, Angelholm, Sweden) and urine test (inspection and urinalysis) in order to detect hemolysis. Primaquine will be stopped if hemolysis

occur, the subject will be observed for daily vital sign, Hb level, and urine until recovery. If worsen, the subject will be referred to the hospital for further management, and given blood transfusion if necessary (Appendix E).

Primaquine for *P. falciparum* will be given as single dose 0.25 mg/kgBW (6-17 kg=1/4 tab, 18-30 kg=1/2 tab, 31-40 kg=3/4 tab). *P. ovale* will be treated as *P. vivax*. Mixed infection with *Pv* will be treated as *Pv*.

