### **6.9. Adverse Event (AE) and Serious Adverse Event (SAE)**

Adverse events (AE) are defined as any untoward and unintended reaction during the study period. AE will be identified and recorded in CRF by field team in collaboration with the teachers and primary health center attendants. These subjects will be given symptomatic treatment as necessary. Specific AE are black urine, gastro intestinal disturbances, blue lips and breathless.

Serious adverse events (SAE) is an AE which becomes serious and could endanger the life of subjects, cause hospitalization/prolong hospitalization, and disability to conduct normal life. The SAE will be recorded in SAE form and reported to PI, clinician coinvestigators, Ethic Committee, and DSMB within 24 hours. SAE' subjects will be treated in RSPP/RS Atambua until recover completely. Complete SAE report will be distributed within one month after the occurrence of SAE.

The observation of AE and SAE will be performed routinely according to the schedule of drug administration (7 days).

If subject is allergic to DHA-PP, second-line treatment (7 days quinine) will be provided by the team in close collaboration with local primary health center (11-17 kg: 3x1, 18-33 kg: 3x1½, 34-40 kg: 3x2). All treatments for AE/SAE which will be given either at the PHC or in hospital, should be reported to the investigator team and being documented in the database.

Treatment will be stopped immediately if any of these following occurs: 1) allergy to the antimalarial regimen being given, 2) Hb drop of more than 20%, 3) active hemolysis which is proven by urine test and Hb drop, 4) Hb drop with warning sign of MetHb (breathless, blue lip/cyanosis, drowsiness, lethargy, palpitation), 5) Any possible SAE related to antimalarial treatment. Hospitalisation is indicated for 2) to 5).

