## **9. Ethical consideration**

### **9.1. The subject risks**

Blood samples collection will only bring minimal risk to the subjects. Only small volume of blood samples (~0.5 ml) will be drawn from the fingertip and using modern equipment which only cause small lesion on the incision site where the lancet or microtainer is introduced. A lancing device of the latest technology will be used to collect blood samples from the skin to collect sufficient blood volume with minimal pain. Blood sample collection will only be performed by trained staff of our investigator team to minimize the possibility of infection or other unlikely adverse events.

The risk of hemolysis in G6PD deficient subjects has been minimized by conducting G6PD screening to all schoolchildren and daily monitoring for hemolysis before and during PQ administration.

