## APPENDIX E. MANAGEMENT OF ACUTE HEMOLYSIS

Any clinical concern of acute hemolysis (sign of anaemia e.g. breathless, fatigue, pale, dark urine, clinical jaundice) or falling haemoglobin during 7 days of treatment should trigger the following:

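### The Appendix J treatment form labels Hb for two days and urine for one, while section 6.8 and Appendix H call for daily checks of both through the primaquine course

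*Protocol*

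**What the plan says.** Section 6.8 sets the rule for treated children: "Monitoring of Hb level and hemoglobinuria for treated subjects will be done daily before and during treatment", using HemoCue for Hb and both inspection and urinalysis for urine. Appendix H puts this into a schedule, with HemoCue, urine colour and urinalysis each at d0 to d7, beside primaquine doses D1 to D7. Section 9.1 relies on "daily monitoring for hemolysis before and during PQ administration" as part of its case that the haemolysis risk has been minimised.

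The Case Report Form in Appendix J has day columns D-1 to D-14 and rows for DHA-PP tablets, primaquine tablets, Hb, urine and symptoms. Its Hb row is labelled "Hb (D-1 sebelum minum obat & D-3" and its urine row "Urin (D-1 sebelum minum obat". The Indonesian phrase means before taking the drug.

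On course length, section 6.8 adds: "The total dose of PQ should be completed within 10 days as the window period". Section 6.9 says "The observation of AE and SAE will be performed routinely according to the schedule of drug administration (7 days", and Appendix E opens with clinical signs of haemolysis or "falling haemoglobin during 7 days of treatment should trigger the following".

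**The concern.** Field staff work from the form. If they follow its labels, they take one Hb reading and no urine test after the first primaquine dose. The one labelled urine test comes before the first tablet, so it can serve as a baseline but cannot show haemolysis caused by the drug.

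The stopping rules in section 6.9 need more than that. Rules 2), 3) and 4) all depend on a measured fall in Hb, and rule 3) is "active hemolysis which is proven by urine test and Hb drop". Rules 2) to 5) also lead to hospitalisation. The regimen is 1 mg/kg daily for 7 days in schoolchildren, and its safety is secondary objective II, so the same readings are both a protection for the child and trial data.

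**Working it through.** The protocol states no figure to reproduce. The check is a count of the days on which each document asks for a measurement.

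**Inputs**
- Appendix H: d0 stands in the same column as primaquine D1, d6 in the column of D7, and d7 is the following day. That gives 8 slots each for Hb and urine. The enrolment HemoCue reading is separate and is not counted.
- Appendix J form: the labels for the Hb and urine rows.
- Assumption: D-1 on the form is the first treatment day. The column sequence and the label placing that reading before the drug both point to this.

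**Side by side, on-time 7-dose course**

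| Appendix H slot | d0 | d1 | d2 | d3 | d4 | d5 | d6 | d7 |
|---|---|---|---|---|---|---|---|---|
| Form column | D-1 | D-2 | D-3 | D-4 | D-5 | D-6 | D-7 | D-8 |
| Primaquine dose | 1 | 2 | 3 | 4 | 5 | 6 | 7 | none |
| Hb and urine in Appendix H | yes | yes | yes | yes | yes | yes | yes | yes |
| Hb label on form | before drug | – | yes | – | – | – | – | – |
| Urine label on form | before drug | – | – | – | – | – | – | – |

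**Counts**
- Hb: 2 of 8 slots labelled; 8 − 2 = 6 are not.
- Urine: 1 of 8 labelled; 8 − 1 = 7 are not.
- Labelled after the first dose: Hb 2 − 1 = 1; urine 1 − 1 = 0.
- Doses given after the last labelled Hb day: doses 4 to 7, which is 4 of 7.

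These figures count days named in a row label. They do not count omitted checks.

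**Course completed late**
- With a 10-day window starting at d0, the last possible dosing day is d9. Section 6.8 requires daily checks during treatment, so d8 and d9 are already covered if dosing continues.
- An on-time course also has a check on the day after the last dose (d7 in Appendix H). For the latest permitted course that day is d10, or D-11 on the form, within the columns to D-14.
- Section 6.8 covers the period before and during treatment, so it does not supply that final check. Appendix H supplies it if d0 to d7 are counted by dose, and does not if they are counted as calendar days.
- The check at issue is therefore at most 1 per delayed child. The protocol gives no rate of delay, so no number of children can be estimated.

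**The case against.** The strongest reply is that the governing text is sound. Section 6.8 and Appendix H agree on daily checks, and the stopping rules act on measurements that section 6.8 orders, not on what a row label says. The form is generic: it is headed for family screening as well as school, lists four species, and its 14 columns match the 14-day low-dose regimen in Appendix B, Table 3. Every day has an open cell in both rows. Section 7.6 has HemoCue results saved and transferred to a computer. Daily symptom rows on the form, including blue lips and urination complaints, give some cover for the warning signs in rule 4).

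Most of this stands, and it limits the point. A reader might infer that children receive doses 4 to 7 without monitoring. The documents do not support that, because every one of those checks remains required. What survives is that the labels name specific days and those days disagree with section 6.8. Having room to write a result is not the same as being asked for one. Section 7.6 also requires HemoCue results to be entered by hand in the Case Report Form, and the protocol describes no electronic record for urine results. A shared form may explain the labels, but no other form with a primaquine row is shown.

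A reader might also infer that the checking period for delayed courses is left open. It is not: section 6.8 sets it, in the same paragraph as the 10-day window. The 7-day wording in section 6.9 and Appendix E can be read as the nominal course length, and Appendix H numbers its slots beside the doses. Only the check on the day after a late last dose is unclear.

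**Conclusion.** The point holds as an inconsistency between a data-collection form and the text it serves. The form's labels prompt 2 of 8 Hb checks and 1 of 8 urine checks, with no urine test after the first dose. Because the form is an operative instruction to field staff on the main hazard of the trial drug, it is worth correcting before use even though sections 6.8 and 9.1 need no change.

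Two limits apply. Section 9.1 promises daily haemolysis monitoring but names neither Hb nor urine; those measurements come from section 6.8 and Appendix H. And nothing shows that checks would be missed in practice, so no effect on event rates or on the safety results can be stated. The conclusion assumes that D-1 is the first treatment day and that no other treatment form exists beyond those shown. The flowchart belonging to Appendix E is not shown, so it has not been assessed.

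**What to change.** In the Appendix J Case Report Form, for 7-day high-dose primaquine courses, relabel the Hb and urine rows: 'daily, from D-1 before taking drug to the day after the last primaquine dose'. The existing columns are sufficient. Courses on other regimens can keep their own label.

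As a minor clarification, add a footnote to Appendix H saying that d0 to d7 follow the doses actually taken. A course completed late within the 10-day window then keeps both the daily checks that section 6.8 already requires and its check on the day after the last dose.

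The cost is rewording one form and adding one footnote. An on-time course gains no check beyond Appendix H. A delayed course gains at most one finger prick and one urine test per child beyond what section 6.8 requires.
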